8.1.1 Serious Adverse Event (SAE)

An adverse event (AE) includes any unforeseen illness or injury or adverse clinical sign (including abnormal laboratory results) related or not to the investigational product. This includes events related to the product or to the comparator, or to the procedures involved.

It will be considered a serious adverse event (SAE) when:

- Causes death.
- It leads to a significant deterioration in the patient's health that results in:
 - Illness or injury that threatens life.
 - A permanent deterioration of a body structure or function.
 - Hospitalization or prolongation of hospitalization.
 - Medical or surgical intervention to prevent a life-threatening illness, injury or permanent disability of a body structure or function.
- Led to fetal distress, fetal death, or a congenital abnormality or birth defect.

Adverse events of interest for this study will be considered:

- Duration of the procedures greater than 1 hour.
- Problems related to the surgical wound.
- Infection.

NOTES:

- Planned hospitalization for a pre-existing condition, or a procedure required by the CIP, without serious deterioration in health, is not considered a serious adverse event.
- A pregnancy is not considered to be a serious adverse event but will be captured in the CRF as a non-serious adverse event to allow follow-up on the outcome of the pregnancy
- Examples for serious deterioration are: cardiac arrest (CPR required), CVA, paralysis, sepsis, amputation, internal/external bleeding, cancer, fracture requiring intervention, myocardial infarction.

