8.1 Adverse Events

The following adverse events will be recorded in the eCRF of the study:

- All serious adverse events.
- All adverse events considered of interest for this study, regardless of their seriousness.

NOTE - As the primary efficacy measure in this study is pain, leg and back pain does not need to be reported as an adverse event unless it meets the definition of a serious adverse event. However, Investigators may, at their discretion, report any pain-related adverse events during the study.

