8.2 Adverse Device Effect (ADE)

An adverse event related to the use of a medical device.

This definition includes adverse events resulting from insufficient or inadequate instructions for use, deployment, implantation, installation, or operation, or any malfunction of the medical device.

This definition includes any event resulting from the use error or from intentional misuse of the medical device.

During this clinical investigation an event should be considered related to the device when it is the result of:

- The device components (e.g. lead, extension, Trial Simulator, Remote).
- The Therapy/simulation.

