8.3 Unanticipated serious adverse device effect (USADE)

An unanticipated serious adverse device effect (USADE) is a serious adverse device effect that was not previously identified in nature, severity, or degree of incidence in the investigational plan or application (including a supplementary plan or application), or any other unanticipated serious problem associated with a device that relates to the rights, safety, or welfare of subjects.

Those known adverse events related to the device, procedure or therapy is listed in the Risk Analysis section.

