8.4 Anticipated serious adverse device effect (ASADE)

A serious adverse device effect which by its nature, incidence, severity or outcome has been previously identified in the risk analysis report.

Untoward medical occurrences that are not unanticipated, i.e. are unsurprising, are identified in the Physician Manual or CIP and ICF.

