8.6 Serious adverse device effect

Adverse device effect that has resulted in any of the consequences characteristic of a serious adverse event.

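### The word 'unforeseen' in the only adverse event definition (8.1.1) conflicts with 8.3 and 8.4 and, read literally, lets a known serious complication fall outside the SAE definition

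*Combined protocol and SAP*

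**What the plan says.** The adverse event definition is the opening sentence of section 8.1.1: "An adverse event (AE) includes any unforeseen illness or injury or adverse clinical sign", whether or not related to the investigational product. The next sentence widens the scope: "This includes events related to the product or to the comparator, or to the procedures involved". The seriousness criteria follow directly and apply to the event just defined.

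Three further terms rest on this one:

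- 8.2, adverse device effect: "An adverse event related to the use of a medical device".
- 8.6, serious adverse device effect: "Adverse device effect that has resulted in any of the consequences characteristic of a serious adverse event".
- 8.4, the anticipated kind of the latter (ASADE), is defined thus: "A serious adverse device effect which by its nature, incidence, severity or outcome has been previously identified in the risk analysis report".

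Other text in section 8 plainly counts foreseen events as adverse events. Section 8.3 says: "Those known adverse events related to the device, procedure or therapy is listed in the Risk Analysis section". Section 8.4 adds: "Untoward medical occurrences that are not unanticipated, i.e. are unsurprising, are identified in the Physician Manual or CIP and ICF".

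The recording rule is in 8.1. The eCRF takes "All serious adverse events" and, whatever their seriousness, the events of interest. Section 8.1.1 lists three of these: a procedure longer than 1 hour, problems with the surgical wound, and infection.

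**The concern.** An adverse event definition for a safety endpoint should not depend on whether the event was expected. Expectedness is a later classification, and this plan makes it in 8.3 and 8.4. Placing 'unforeseen' in the base definition puts that classification ahead of recording. A site following the words has textual support for not calling a recognised serious complication an adverse event.

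At stake are secondary endpoint 5.3.8 (adverse events related to the procedures, both groups) and the safety data that reach the DSMB described in 3.8. Section 7.2 leaves the assignment open to the investigators. A definition that calls for judgement at the point of recording therefore gives room for ascertainment to differ between the groups.

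**Working it through.** No arithmetic applies. The check traces the definitions and then asks whether another provision closes the gap.

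**1. The chain of definitions.** An ASADE (8.4) must be a serious device effect. A serious device effect (8.6) must be a device effect, and a device effect (8.2) must be an adverse event. So every ASADE is an adverse event under 8.1.1.

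**2. Literal reading.** Suppose 'unforeseen' is a necessary condition for an adverse event. Then every ASADE is unforeseen. By 8.4 every ASADE has also been identified beforehand. No event meets both conditions, so on this reading the category has no members.

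**3. The same step for SAEs.** The seriousness criteria in 8.1.1 qualify an adverse event. On the literal reading, a known complication is not an adverse event and so cannot be an SAE, however grave its outcome.

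**4. Does the recording rule in 8.1 close the gap?** It sets no foreseeability condition of its own. But it asks for SAEs, and an SAE is an adverse event as 8.1.1 defines it. The rule inherits the qualifier.

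**5. Does expedited reporting close it?** Section 7.9 gives failure to report SAEs or USADEs within 24 hours as a possible reason for suspending a site. Under 8.3 a device effect already identified in nature, severity and incidence is not a USADE. If the site does not regard it as an SAE either, neither label applies.

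**6. Does the vigilance route in 8.8 close it?** It sorts reportable incidents by outcome and has no 'unforeseen' test. However, it defines an incident as a malfunction, failure or deterioration of the product, or a deficiency in its labelling or instructions. A recognised complication of a device that worked as designed is not clearly covered.

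**7. Which events does the word affect?**

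| Known event | Recorded under 8.1? | Affected by 'unforeseen'? |
|---|---|---|
| Infection, wound problem, procedure over 1 hour | Yes, as a named event of interest | No |
| Other, non-serious | In general no; 8.1 does not ask for it | No; the 8.1 rule already leaves it out |
| Other, serious | Yes, if it counts as an SAE | Yes, on the literal reading |

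Two small exceptions to the middle row do not change the result: 8.1.1 has pregnancy captured as a non-serious event, and 8.1 lets investigators report pain-related events at their discretion.

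**8. Can a site look up what is foreseen?** Section 8.3 points to a Risk Analysis section, but the index lists none. Section 8.4 points to a risk analysis report, the Physician Manual, the CIP and the consent form. The report and the manual are not among the documents reviewed, and the consent pages were removed from this copy. What counts as already listed could therefore not be checked.

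**The case against.** The strongest reply is that the literal reading is not forced. The verb in 8.1.1 is 'includes', not 'means'. 'Unforeseen' may attach only to illness, or to illness and injury, leaving clinical signs unqualified. The second sentence brings in product, comparator and procedure events with no such limit. A long procedure is none of the three things named, yet it is listed as an adverse event of interest, so the opening sentence is not exhaustive. Sections 8.3 and 8.4 speak of known and unsurprising events. All of this stands. It shows what the sponsor meant, and it also shows that 8.1.1 says something different, in the one sentence a site would consult.

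A reader might go further and infer any of the following. The documents do not support them.

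- **That known complications in general escape recording because of this word.** Three kinds are named for recording regardless, and most non-serious ones are left out by the 8.1 rule. Deleting the word would not bring those into endpoint 5.3.8.
- **That the plan has in effect abolished the ASADE category.** The plan keeps and defines it. The category is empty only if 'includes' is taken as exhaustive.
- **That steroid complications help to empty that category.** ASADEs are device effects, so complications of the steroid alone do not bear on it.
- **That investigators aware of the assignment are given the decision on what was foreseen.** No passage says so. Sections 8.3 and 8.4 refer anticipation to documents. What remains is narrower: 8.1.1 names no reference list for its own qualifier, and the assignment is open to the investigators.

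**Conclusion.** The concern holds as an internal inconsistency worth correcting. The only adverse event definition carries a qualifier that contradicts 8.3 and 8.4, and neither 8.1 nor 8.8 clearly repairs it. Read literally, it allows a known serious complication of the procedure or device to be treated as not an adverse event and so not an SAE, and it leaves no possible ASADE.

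The reach is limited mainly to known serious complications other than infection and wound problems. The number of events affected cannot be estimated, because the documents give no expected complication rates. It would be zero if every site followed the evident intent of 8.3 and 8.4. The conclusion assumes only that some site might apply 8.1.1 as worded; nothing in the documents shows that any site has done so.

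**What to change.** In 8.1.1, replace 'unforeseen' with 'untoward, whether or not anticipated'. 'Untoward' is already used in 8.4. Add one sentence: events that meet the recording rule in 8.1 are recorded even when they are listed as known risks, and serious device effects among them are then classified as anticipated or unanticipated under 8.3 and 8.4. Repeat this in the CRF guidance.

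The added sentence should stay within the existing 8.1 rule. A broader instruction to record every known-risk event would contradict 8.1 for non-serious events and would widen safety collection, which is a separate decision.

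The cost is one phrase, one sentence and a line of guidance. The downside is possibly a few more SAE forms and a slightly higher reported count.

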5.3 Secondary Endpoints

- 5.3.1. Change from Baseline in pain at 1, 2 and 4 months (assessed by Visual Analogue Scale, VAS).
- 5.3.2. Change from Baseline in disability at 1, 2 and 6 months (assessed by Oswestry Disability Index, ODI).
- 5.3.3. Change from Baseline in health survey at 1, 2, 4 and 6 months (assessed by Short Form Health Survey, SF-12).
- 5.3.4. Change from Baseline in neuropathic pain at 1, 2 and 6 months (assessed by Douleur Neuropathique 4 Questions, DN4).
- 5.3.5. Assessment of improvement of pain with experimental procedure at 1, 2, 4 and 6 months (assessed by Patient Impression of Improvement, PGI-I).
- 5.3.6. Incidence of unanticipated adverse device effects.
- 5.3.7. Change in opioid intake in 6 months.
- 5.3.8. Adverse events related to procedures (experimental group and control group).
- 5.3.9. Assessment of subject satisfaction with experimental procedure at 2 and 6 months.

6. - ELIGIBILITY CRITERIA

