8.7 Severity

The Investigator will use the following definitions to rate the severity of each adverse event:

- Mild: Awareness of a sign or symptom that does not interfere with the subject's usual activity or is transient, resolved without treatment and no sequelae.

- Moderate: Interferes with the subject's usual activity or requires symptomatic treatment.
- Severe: Symptom(s) causing severe discomfort with significant impact of the subject's usual activity and requires treatment.

8.8 Reporting.

According to current regulations, professionals must report those incidents that are associated with a medical device or with the information provided with the product and that incident is such that it has caused death or a serious deterioration in health, or if it occurs again it can cause them.

An incident is understood to be any malfunction, failure or deterioration of the characteristics or operation of a product, as well as any deficiency in the labelling or in the instructions for use that could or have led to death or serious deterioration of the condition health of a patient or a user. The types of adverse incidents that must be reported are the following:

1. Those that lead to death.
2. Those that give rise to a serious deterioration of the state of health of the patient, user or other person, such as:

- Illness or injury with threat to life.
- Permanent deterioration of a bodily function or permanent damage to a body structure.
- Process that requires medical or surgical intervention to avoid permanent deterioration of a bodily function or permanent damage to a body structure.

3. Potential incidents, which are those that could have led to death or a serious deterioration of health, but that have not occurred due to fortunate circumstances or the intervention of health personnel.

These incidents must be reported by the investigators. They must notify the sponsor of any serious incidents that may be related to the devices involved in the development of the investigation, through Annex III available at:

<https://www.aemps.gob.es/vigilancia/productosSanitarios/vig-prof-nota.htm#II>

And the sponsor must evaluate them and notify them to the surveillance points of medical devices of the CCAA, in accordance with the general guidelines established by the Medical Device Surveillance System for the notification of adverse incidents:

<https://www.aemps.gob.es/surveillance/healthproducts/professional-monitoring.htm>

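### Section 8.1 records only serious events and a short list of events of interest, so it does not supply the procedure-related adverse event endpoint in 5.3.8, least of all for non-serious nerve deficit

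*Combined protocol and SAP*

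**What the plan says.** Section 8.1 is the only place that states which adverse events enter the eCRF. It names two groups: all serious events, and "All adverse events considered of interest for this study, regardless of their seriousness". Section 8.1.1 then gives the list under "Adverse events of interest for this study will be considered": a procedure lasting more than an hour, surgical wound problems, and infection. The list is not marked as open-ended.

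Two additions lie outside the list. A note in 8.1.1 says that a pregnancy "will be captured in the CRF as a non-serious adverse event". A note in 8.1 leaves pain-related events to the investigator's discretion.

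The seriousness criteria in 8.1.1 cover the graver nerve injuries. They include "A permanent deterioration of a body structure or function", hospitalisation, and intervention to prevent permanent disability. Paralysis is given as an example of serious deterioration.

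Section 5.3 sets two safety endpoints that bear on this: 5.3.6, "Incidence of unanticipated adverse device effects", and 5.3.8, "Adverse events related to procedures (experimental group and control group". Neither mentions seriousness.

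**The concern.** An endpoint can count only what the case report form holds. If sites apply 8.1 literally, a procedure-related event that is neither serious nor on the short list is not entered, although 5.3.8 is meant to count it.

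Nerve effects are where this matters most. The catheter electrode treats nerve roots inside the spinal canal, and Section 4 names heating to neurolytic temperatures there as a possible source of substantial complications. Yet no event of interest is neurological. New numbness or weakness that is not permanent, and that needs neither hospitalisation nor preventive intervention, falls outside 8.1.

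Two consequences follow. A low count could mean few events or little recording, and the report could not tell which. Also, Section 7.2 leaves investigators aware of the allocation, so recording that depends on their discretion could differ between arms, in either direction.

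**Working it through.** **1. Does 8.1 supply each provision that might need it?**

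| Provision | What it needs | Does 8.1 supply it? |
|---|---|---|
| 5.3.8 | Procedure-related adverse events in both arms, any seriousness | No. Non-serious events outside the list are missing |
| 5.3.6 | Unanticipated device effects | Depends. Section 8.3 defines only the serious kind; if 5.3.6 means those, 8.1 records them; if not, it falls short |
| 8.2 | Defines a device effect as "An adverse event related to the use of a medical device" | No conflict. It is a definition, not a recording instruction |
| 8.7 | "The Investigator will use the following definitions to rate the severity of each adverse event", with a mild grade | No conflict. It can mean each recorded event, and a recorded infection can be mild |

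The clear mismatch is with 5.3.8. Sections 8.2 and 8.7 fit a wider intention but do not contradict 8.1.

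**2. What else could capture a non-serious sensory or motor deficit?**

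- Follow-up and Unscheduled visits (7.5) ask about adverse events and document applicable information on a CRF. What is applicable is not defined there.
- Section 7.6 assesses safety at all visits, in general terms.
- DN4 items 6, 8 and 9 record numbness and reduced sensation to touch and pinprick. They do so at Baseline, months 1, 2 and 6 and any Unscheduled visit, but only in the painful area and as part of a pain score. The DN4 has no motor item.
- Leg motor function is checked before discharge in both arms (9.1, 9.2). Table 1 lists no later motor examination.

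What remains without an assured route is non-serious motor deficit, deficit outside the painful area, and sensory change that resolves before the next DN4.

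**3. How much could it matter?**

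The plan's one relevant figure is 62 per arm (7.3). It reproduces: a two-sided t-test with difference 20 mm, SD 30 mm, alpha 0.05 and power 90% needs 49 evaluable per arm, and 49 / 0.80 = 61.25, rounded up to 62.

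The plan gives no rate of nerve deficit and no recording share, so both are assumed. Let r be the per-patient risk of a non-serious deficit and c the share recorded. Recording is taken as independent between patients, and all 62 are taken as treated and followed.

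Chance that an arm shows no event = (1 − r × c)^62:

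| r | Expected events (62 × r) | c = 100% | c = 50% | c = 25% | c = 0 (8.1 taken literally) |
|---|---|---|---|---|---|
| 2% | 1.24 | 28.6% | 53.6% | 73.3% | 100% |
| 5% | 3.1 | 4.2% | 20.8% | 45.8% | 100% |
| 10% | 6.2 | 0.1% | 4.2% | 20.8% | 100% |

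One-sided 95% upper bound on r after a zero count = (1 − 0.05^(1/62)) / c:

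- c = 100%: 1 − 0.05^(1/62) = 4.7%
- c = 50%: 4.7% / 0.50 = 9.4%
- c = 25%: 18.9% (from the unrounded 4.717%)
- c = 0: no bound exists

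With 20% losses, 62 × 0.80 ≈ 50 patients remain, and the full-recording bound becomes 1 − 0.05^(1/50) = 5.8%.

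**The case against.** The best defence is that the plan has several routes by which such an event could be written down. Visits, including Unscheduled visits, ask about adverse events and have a CRF to fill in. Early withdrawal (7.7) triggers an adverse event assessment that is documented on a CRF. Section 7.10 defines a population with adverse event capture in mind. Section 3.8 sets up an independent DSMB. A patient who returns with new numbness may have an Unscheduled visit with a DN4. Serious nerve injury is covered in any case. The eCRF adverse event page and the DSMB charter are not in the documents and may be broader.

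Much of this stands. It shows that some events may be captured. It does not show that they must be, because none of these sections widens 8.1, and a DSMB can review only what reaches it.

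Three stronger readings are tempting, and the documents do not support them.

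- A reader might infer that 8.1 conflicts with 5.3.6, 8.2 and 8.7 as well as 5.3.8. As set out above, 8.2 and 8.7 can stand beside 8.1, and 5.3.6 depends on how it relates to 8.3.
- A reader might infer that mild nerve effects will certainly be lost. The routes above make this a risk whose size depends on site practice.
- A reader might infer that nerve harm is likely. Section 4 reports no complications with voltage-controlled epidural treatment, and the plan limits temperature to 42 °C. The point is about counting, not about expected harm.

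The objection that the numbers rest on assumed r and c is also fair. They illustrate the problem and are not evidence about this trial.

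**Conclusion.** The point holds in limited form. The recording rule in 8.1 and 8.1.1 is narrower than endpoint 5.3.8, so following it as written under-records a stated secondary safety endpoint. Endpoint 5.3.6 is affected too, unless it is confined to the serious unanticipated effects of 8.3. The most relevant gap is non-serious new or worsened sensory or motor deficit.

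This mismatch follows from the text and needs no assumed rate. Its size cannot be derived from the plan. The useful benchmark is that zero events in 62 patients supports an upper bound of 4.7% only with full recording, and supports none if 8.1 is applied literally. The primary pain comparison and the sample size are unaffected. It should be corrected because the change is small and two arms' safety counts depend on it.

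**What to change.** Make two additions.

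1. In 8.1, add a third recorded group: *All adverse events related to the device or procedure, regardless of seriousness.* This supplies 5.3.8, and supplies 5.3.6 under either reading.
2. In the 8.1.1 events of interest, add: *New or worsened sensory or motor deficit, inside or outside the painful area, whether or not serious.* This line does not depend on a judgement of relatedness.

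The second line alone would not be enough, since other non-serious procedure-related events would still fall outside 8.1.

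The cost is two lines of text and the matching eCRF entry. Visits already ask about adverse events, so no new visit, examination or patient is needed. The downside is a few more events to record. Some will reflect the underlying disease, and an investigator who knows the allocation will still judge what is new, worse or related.

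A descriptive table by arm of patients who move from negative to positive on DN4 items 6, 8 or 9 is optional. It covers the painful area only and does not replace either line.

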The electrode will be connected to an output of the RF generator (Cosman RFG-4-120V/GF RF Generator). To provide a monopolar PRF operation, a ground pad (Cosman DGP-PM-10) will be placed on a shaved muscle part of the posterolateral thigh skin and connected to the reference socket of the RF generator with voltage 0 for 240 seconds (to ensure single-blind).

Intravascular and subdural placement will be ruled out by injecting 1-1.5 ml of non-ionic radiographic contrast (180 mg of iohexol per ml) through the integral injection port of the electrode under live fluoroscopy. Subsequently, betamethasone 12 mg will be administered.

After treatment, the needle and electrode will be removed. A sterile dressing will be applied over the needle insertion site. The patient will be monitored (visualized by fluoroscopy) while the sedation is removed, the motor dysfunction of the leg is verified and then the patient will be discharged.

9.2 Experimental Group. Epidural Pulsed Radiofrequency.

A radiopaque, guidable radiofrequency electrode (Cosman RCE-E401519-P) will bend slightly at a 45° angle proximal to its metal tip and then be inserted through the needle. The electrode shall include an active 20/15 mm gauge tip, a 19/40 cm gauge shaft, a rounded distal point temperature sensor, an injection port and an integral generator connection. The electrode will be visualized by fluoroscopy as it is guided in the epidural space from the sacral canal to the lumbar vertebral canal. The electrode will be connected to an output of the RF generator (Cosman RFG-4-120V/GF RF Generator). To provide a monopolar PRF operation, a ground pad (Cosman DGP-PM-10) will be placed on a shaved muscle part of the posterolateral thigh skin and connected to the reference socket of the RF generator.

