The active tip of 15 mm of the electrode will be placed in the internal aspect of the pedicle in each of levels L4, L5 and / or S1, on the right or left side, according to the patient's pain distribution (Figure 1). Intravascular and subdural placement will be ruled out by injecting 1-1.5 ml of non-ionic radiographic contrast (180 mg of iohexol per ml) through the integral injection port of the electrode under live fluoroscopy. At each treated level, motor stimulation (50 Hz, 1 ms) of less than 0.4 volts will reproduce the patient's pain and motor stimulation (2 Hz, 1 ms) of less than 0.6 volts will result in a contraction muscle in the leg. The pulsed radiofrequency will be applied for 240 seconds (4 minutes), where the pulses of 45 volts and 20 milliseconds (ms) will be administered at 2 Hz (pulses per second) and the pulse width will be regulated to maintain the temperature at 42 °C or less. (E-dose = Vary Width). The steady-state impedance and current will be measured for each PRF epidural treatment at L5 and S1 levels using the 20-gauge, 15 mm active tip.

After the experimental treatment, the needle and electrode will be removed without injecting or any other substance capable of producing pain relief. A sterile dressing will be applied over the needle insertion site. The patient will be monitored while the sedation is removed, the motor dysfunction of the leg is verified and then the patient will be discharged.

10. - PRACTICAL CONSIDERATIONS AND ETHICAL ASPECTS

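### A procedure lasting over 1 hour is listed as an adverse event of interest, so endpoint 5.3.8 can count events in which no patient was harmed, possibly more often in the experimental arm

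*Combined protocol and SAP*

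**What the plan says.** Section 8.1.1 describes the concept first: "An adverse event (AE) includes any unforeseen illness or injury or adverse clinical sign (including abnormal laboratory results) related or not to the investigational product". The next sentence extends it to events related to the product, the comparator or the procedures. The section then lists three adverse events of interest: "Duration of the procedures greater than 1 hour", surgical wound problems, and infection.

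Section 8.1 sets what goes into the eCRF: all serious adverse events, and "All adverse events considered of interest for this study, regardless of their seriousness". Non-serious leg and back pain need not be reported.

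Endpoint 5.3.8 is "Adverse events related to procedures (experimental group and control group"). Section 8.7 has the investigator rate each adverse event as mild, moderate or severe, by symptoms, interference with activity and need for treatment.

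The two procedures are described in section 9:

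- **Control (9.1):** the electrode is guided to the lumbar canal and the ground pad is "connected to the reference socket of the RF generator with voltage 0 for 240 seconds (to ensure single-blind"). A contrast check and betamethasone follow.
- **Experimental (9.2):** "The active tip of 15 mm of the electrode will be placed in the internal aspect of the pedicle in each of levels L4, L5" and/or S1, with stimulation testing at each treated level. "The pulsed radiofrequency will be applied for 240 seconds (4 minutes"), without saying whether that is per level or in total.

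Section 4 gives 480 s at each level for what it calls the present study.

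**The concern.** Procedure time is a process measure. Listed as an adverse event of interest, it turns an uneventful 65-minute procedure into a recorded adverse event. Such an event is procedure-related by nature, so it falls within 5.3.8 unless a rule excludes it, and the plan has none.

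Two features make this more than a labelling matter. First, the list of events of interest has only three items and most pain events are exempt, so one process measure could make up much of the non-serious count. Second, the steps that would lengthen a procedure are not described equally for the two arms. A reader of a two-arm adverse event table could see an excess in the experimental arm that reflects the number of levels treated and not harm.

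What is at stake is the reading of one secondary safety endpoint. The primary endpoint and the sample size are not affected.

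**Working it through.** **Step 1. Does the item fit the plan's own terms?**

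| Requirement | Uneventful procedure over 1 hour |
|---|---|
| 8.1.1: illness, injury or adverse clinical sign | None present |
| 8.7 mild: a sign or symptom that is transient or does not interfere with activity | No sign or symptom to rate |
| 8.7 moderate: interference with activity, or symptomatic treatment | None |
| 8.7 severe: severe discomfort and need for treatment | None |
| 8.1: record every event of interest | Must be recorded |
| 5.3.8: related to the procedure | Yes, by nature; no exclusion rule |

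The item must be recorded, can enter the endpoint and cannot be graded. This needs no assumption.

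**Step 2. Do the listed steps differ by arm?**

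| Step | Control (9.1) | Experimental (9.2) |
|---|---|---|
| Epidural needle, guided electrode, contrast check, generator and ground pad | Yes | Yes |
| Generator period | 240 s at zero voltage | 240 s, per level or total not stated |
| Placement at each of L4, L5 and/or S1 | Not described | Yes |
| Stimulation testing at each treated level | Not described | Yes |
| Steroid injection | Betamethasone | None as 9.2 is written, although the Summary gives steroids to both arms |

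**Step 3. Excess generator time.** The plan gives no figure for procedure time that could be reproduced. The only computable difference is generator time:

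excess (min) = (levels × seconds per level − 240) / 60

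| Reading | 1 level | 2 levels | 3 levels |
|---|---|---|---|
| 240 s per level | (240 − 240)/60 = 0 | (480 − 240)/60 = 4 | (720 − 240)/60 = 8 |
| 480 s per level (section 4) | (480 − 240)/60 = 4 | (960 − 240)/60 = 12 | (1440 − 240)/60 = 20 |
| 240 s in total | 0 | 0 | 0 |

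Time for placement at each level and for stimulation testing is additional, and the documents do not state it.

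**Step 4. Can the effect on the count be sized?** Only under assumptions from outside the documents. Let control duration be normal with mean m of 35, 45 or 55 min and SD s of 10 or 15 min. Shift all 62 experimental patients by d minutes:

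extra events = 62 × [P(Z > (60 − m − d)/s) − P(Z > (60 − m)/s)]

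Example with m = 45, s = 15, d = 8: P(Z > 1.00) = 0.159 in control and P(Z > 0.47) = 0.320 in experimental, so 62 × 0.161 = 10.0.

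| Shift d (min) | Extra events among 62, over the six assumed combinations |
|---|---|
| 0 | 0 |
| 4 | 0.7 to 9.4 |
| 8 | 2.4 to 19.2 |
| 12 | 5.6 to 27.9 |
| 20 | 18.7 to 38.7 |

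With an assumed mean of 30 and SD of 10, a shift of 8 min moves the proportion over 1 hour only from 0.1% to 1.4%, which is 62 × 0.013 = 0.8 events. A common shift also treats every patient as having the same number of levels. The range shows that the assumptions determine the result, so none of these figures is an estimate for this trial.

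**The case against.** The strongest reply has four parts.

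1. **The definition is open.** It says what an adverse event includes and goes on to cover events tied to the procedures. With sedation and fluoroscopy in use, flagging a long procedure in advance is a defensible choice. This stands as a reason to keep capturing duration. It does not make elapsed time gradable under 8.7, and relatedness to a procedure describes cause without supplying an illness, injury or sign.

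2. **The arms are closely matched.** Control has the same needle, electrode guidance, contrast check and generator connection, with a 240 s sham. Generator time is equal if one level is treated at 240 s or if 240 s is the total. As 9.1 and 9.2 are written, only control has a steroid step, a possible small offset; that text conflicts with the Summary and must be reconciled. This largely stands. A reader might infer that the experimental procedure is longer by design, or that 5.3.8 is biased against that arm. The documents support neither as a stated fact: there are no total times, and nothing shows that either procedure approaches 1 hour. What remains is a likely direction, because placement and stimulation testing by level appear only in 9.2.

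3. **No pooled count or test is specified.** Section 13 gives descriptive frequencies and no between-arm adverse event test, and a table by event type would show duration on its own line. This stands, and it limits the consequence. But 5.3.8 is a single undivided endpoint, and nothing requires that layout.

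4. **A longer procedure would be a true difference between arms.** Agreed, but it is a difference in duration and should be reported as one.

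**Conclusion.** The point holds in a limited form. On the text alone, 8.1.1 makes an ungradable process measure a recordable adverse event, and nothing keeps it out of 5.3.8. That part rests on no assumption.

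The effect on the comparison between arms is a possibility with a likely direction and an unknown size. It may inflate the experimental count, mainly in multi-level patients. The computable part is 0 to 8 minutes of excess generator time at 240 s per level, 0 if 240 s is the total, and 4 to 20 minutes at 480 s per level. The documents do not say how many patients are treated at each number of levels or how long either procedure takes, so no excess event rate can be derived from them.

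Severity is minor: one secondary safety endpoint with no planned test. Confidence is moderate.

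**What to change.** - Add procedure start time, end time and number of levels treated to the treatment-visit CRF.
- Summarise duration by arm, including the proportion over 1 hour, as a procedural variable apart from adverse events.
- State that the 5.3.8 count excludes duration alone. At minimum, show 5.3.8 with and without it.
- State that any clinical consequence of a long procedure remains reportable under 8.1.1.
- The sponsor should reconcile the 240 s in 9.2 with the 480 s per level in section 4, say whether 240 s is per level or in total, and reconcile the steroid statements in the Summary and 9.2. No view is taken here on which is right.

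The reporting change costs the added CRF fields, one descriptive table and a sentence defining the endpoint. The 1-hour flag survives as a procedural summary, so the information is kept provided the new fields are completed. The 62 per group is unchanged.
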